1. SYNOPSIS

Name of Sponsor/Company:			
Intercept Pharmaceuticals, Inc.			
Name of Investigational Product:			
Obeticholic Acid			
Name of Active Ingredient:			
Obeticholic acid (OCA); 6α-ethyl-chenodeoxycholic acid; (6-ECDCA); INT	-747; DSP-1747		
Title of Study:			
Replicate Studies Evaluating the Effectiveness of Obeticholic Acid on Hepatic Real-World Outcomes in Patients with Primary Biliary Cholangitis (HEROES PBC)			
Investigators and/or Study Center(s):			
[name] (Target, University of North Carolina - Chapel Hill)			
[name] (Target, Duke University)			
[name] (Target)			
[name] (University Health Network)			
[name] (University Health Network)			
[name] (Optum)			
[name] (Syneos Health)			
[name] (Syneos Health)			
Studied Period (years):	Phase of Development:		
Estimated initial patient inclusion date 01 Jun 2015 Phase 4			
Estimated date last patient observation: 31 Dec 2021			
Objectives:			
Primary Objective			
To evaluate the effect of OCA treatment on time to the first occurrence of th	e composite endpoint of all-cause death,		

Io evaluate the effect of OCA treatment on time to the first occurrence of the composite endpoint of all-cause death, liver transplant, or hospitalization for hepatic decompensation in PBC patients in 2 data sources: Global PBC registry and Komodo Health claims database.

Exploratory Objectives:

To evaluate the effect of OCA treatment on time to the first occurrence of individual components of the composite endpoint (outlined below):

- All-cause death
- Liver transplant
- Hospitalization for hepatic decompensation based on the first occurrence of:
 - Variceal bleed
 - Ascites (including hepatic hydrothorax and spontaneous bacterial peritonitis)
 - Hepatic encephalopathy

Methodology:

These are replicate, observational, retrospective cohort studies of patients with PBC who failed ursodeoxycholic acid (UDCA) treatment using 2 real-world data sources: the Global PBC registry (Study 747-404) and the Komodo Health United States (US) claims database (Study 747-405). All analyses will be conducted separately by data source (ie, not pooled). The primary endpoint is time to first occurrence of all-cause death, liver transplant, or hospitalization for hepatic decompensation. The analytic approach is a nested target trial emulation design.

The Komodo Health database contains administrative claims from >350 US payers, including commercial (63%); Medicaid (23%); Medicare (10%); dual eligible (<1%); and other (2%). Data are tokenized to allow for patient tracking across payers. Komodo Health claims will be linked through Datavant tokenization to Quest Diagnostics and LabCorp laboratory data, the US National Death Index (NDI), and the Organ Transplant Network (OPTN) transplant registry for additional information and outcome verification. The database contains >100,000 patients with a PBC diagnostic code. The Global PBC registry includes >5,000 patients with PBC recruited from 17 liver centers across 8 countries in Europe and North America. It utilizes the CASTOR trial platform for electronic case report form (eCRF) collection of medical history, clinical events, and laboratory and treatment data.

All patients who meet diagnostic criteria for PBC in each database between 01 Jun 2015 and 31 Dec 2021 and who meet all eligibility criteria will be considered for these studies. The OCA treatment evaluation period will be from 01 Jun 2016 (based on first country approval by Food and Drug Administration on 27 May 2016). The Komodo Health database is US-specific and the Global PBC registry includes the US and multiple other countries with later approval dates. The Sponsor has applied the date of first global approval of 01 Jun 2016 for both studies. The first date of prescription of OCA after inadequate UDCA response (ALP>upper limit of normal [ULN] and/or total bilirubin [TB]>ULN after >270 days of treatment) or UDCA intolerance (discontinued UDCA after <90 days despite ALP>ULN and/or TB>ULN) will be defined as the index date for OCA-treated PBC patients. The dates of evidence of inadequate UDCA response or UDCA intolerance during which OCA is not utilized will be used as an index date for the non–OCA-treated comparator group.

Each time a patient meets the UDCA inadequate response/intolerance definition or the definition of OCA initiation, in addition to all other eligibility criteria, they will contribute an index to the study. Therefore, patients may contribute multiple control indices, and may contribute control indices before OCA initiation, but can contribute only one OCA initiation index. The non–OCA-treated patient indices will be weighted to have the same baseline covariate distribution as the OCA-treated patients at the time of OCA initiation, thus allowing for the estimation of the effect of treatment in the treated patients. The pre-index period is defined as 12 months prior to the index date, and follow-up is until the first occurrence of any component of the composite endpoint. Patients will be censored at dropout/disenrollment from the database, discontinuation of OCA (+90 days), initiation of fenofibrate or bezafibrate, initiation of OCA (for the non–OCA-treated patient -indices), unapproved OCA dose (>10 mg once daily [QD]) for those treated with OCA, or the end of the study period (31 Dec 2021), whichever comes first.

Schematic Diagram Studies 747-404/405:

Number of Patients (planned):

Komodo Health: In the current Komodo Health database, there are 395 patients who meet all of the following criteria for the OCA treatment group:

- Meet PBC claims diagnostic criteria (1 inpatient or 2 outpatient claims)
- Have evidence of UDCA failure
- Have initiated OCA treatment

There are 5916 patients who meet all of the following criteria for the control group (OCA-eligible but not currently OCA-treated)

- Meet PBC claims diagnostic criteria (1 inpatient or 2 outpatient claims)
- Have at least 270 days of UDCA use before elevated ALP and/or TB inclusive of up to 4 instances of elevation (inadequate response) or <90 days UDCA use despite elevated ALP and/or bilirubin (intolerant)
- Have elevated ALP >ULN and/or TB >ULN

The Komodo Health database has not yet been linked to LabCorp laboratory database. It is anticipated that the number of patients in each group will approximately double with the availability of LabCorp data.

Global PBC registry: The Global PBC registry data are currently being refreshed. A previous analysis identified 344 patients who had initiated OCA. Among the >5000 patients not treated with OCA, it is anticipated that >2200 will meet criteria for UDCA failure and for inclusion in the control group (Corpechot 2008, Kumagi 2010).

Diagnosis and Main Criteria for Inclusion:

The treatment group will be patients with PBC with a history of inadequate response or intolerance to UDCA who initiated OCA in the study window. The control group will be PBC patients with a history of inadequate response or intolerance to UDCA who were eligible but not treated with OCA (or off-label fibrates) in the study window.

Key Inclusion Criteria

A patient who meets **all** of the following criteria for a given index date is eligible for inclusion:

- Definite or probable PBC diagnosis
 - Global PBC registry (consistent with American Association for the Study of Liver Diseases [AASLD] and the European Association for the Study of the Liver [EASL] practice guidelines; Lindor 2009, EASL 2009): presence of ≥2 of the following 3 diagnostic factors:
 - EASL 2009): presence of 20 of the following 3 diagnostic factors.
 History of elevated ALP levels for at least 6 months.
 - History of elevated ALP levels for at least 6 months
 - Positive antimitochondrial antibody (AMA) titer
 - Liver biopsy finding consistent with PBC
 - Komodo Health claims data: one of the following (Meyers 2010):
 - ≥1 inpatient claim with a PBC admission diagnosis at any position (ie, primary, secondary diagnosis, etc.)
 - ≥ 2 outpatient claims with a PBC diagnosis on separate days
 - Inadequate response or intolerant to UDCA (see definitions below)
- Age ≥ 18 years at the index date
- Continuous enrollment and evaluable data for at least 12 months before the index date (inclusive)

Key Exclusion Criteria:

A patient who meets **any** of the following criteria for a given index date is not eligible for inclusion:

- History or presence of the following concomitant liver diseases before the index date (inclusive), including:
 - Acute or chronic hepatitis C virus infection
 - Acute or chronic hepatitis B infection
 - Primary sclerosing cholangitis
 - Active alcoholic liver disease
 - Hepatocellular carcinoma
 - Hepatorenal syndrome
 - Hepatopulmonary syndrome
 - Portopulmonary syndrome
 - Nonalcoholic steatohepatitis (NASH)
- History of non-skin malignancy or melanoma before the index date (inclusive)
- History of HIV before the index date (inclusive)
- Medical conditions that may cause non-hepatic increases in ALP such as:
 - Paget's disease during the 12-month period before the index date (inclusive)
 - Fractures within 3 months before the index date (inclusive)

- Patients with laboratory values indicative of hepatic decompensation or significant hepatobiliary injury before the index date (inclusive)
 - \circ TB >3 mg/dL
 - \circ ALP >10x ULN
 - ALT and/or AST >10x ULN
- History of liver transplant before the index date (inclusive)
- Evidence of OCA, fenofibrate, or bezafibrate use before the index date (inclusive)
- History or presence of any of the following hepatic decompensating events before the index date (inclusive):
 - Variceal bleeding
 - o Ascites
 - Hepatic hydrothorax
 - o Spontaneous bacterial peritonitis
 - Hepatic encephalopathy

Definitions:

- UDCA failure:
 - Inadequate response requires both of the following:
 - At least 1 measure of ALP>ULN and/or TB>ULN
 - \geq 270 days of UDCA treatment prior to ALP and/or TB elevation
 - \circ Intolerant:
 - A maximum of 90 days of UDCA use with ALP>ULN and/or TB >ULN

Group Assignments:

- **Treatment group (OCA-treated)**: ≥1 prescription or medical claim for OCA at or after UDCA failure date. The first date will be the one index date.
- Control Group (Non-OCA-treated but eligible for OCA): Each date corresponding to evidence of a patient meeting the definition of UDCA inadequate response or intolerance in which the patient meets the inclusion and exclusion criteria and does not initiate OCA will be an index date for the non–OCA-treated patient group. Patients may contribute indices to this group before they initiate OCA, but not after OCA index.

Study medication, Dosage and Mode of Administration:

OCA tablet, 5 mg to 10 mg, once daily, oral administration

Patients may down titrate to <5 mg daily, but are censored if dose exceeds 10 mg per day.

Study drug is not provided nor administered by the Sponsor but is recorded by either administrative claim or registry CRF.

Duration of treatment will range from 1 to 67 months

Reference Therapy, Dosage and Mode of Administration:

Not applicable

Data Sources

The data source for each analysis will include one of the following:

1. Komodo Health US administrative claims database linked to the following:

- Laboratory measures (Quest Diagnostics and LabCorp)
- National Death Index (US NDI)
- National transplant registry (OPTN registry)

Or

2. Global PBC registry

Criteria for Evaluation:

Primary Outcome:

As-treated time to the first event of the composite endpoint of all-cause death, liver transplant, or hospitalization for hepatic decompensation, whichever occurs first.

Exploratory Outcomes:

As-treated time to the first occurrence of individual components of the composite endpoint:

- All-cause death
- Liver transplant
- Hepatic decompensation requiring hospitalization assessed through claims or registry CRF and defined as first occurrence of:
 - Variceal bleed
 - Ascites (including hepatic hydrothorax and spontaneous bacterial peritonitis)
 - Hepatic encephalopathy

Exposure Variable:

The exposure variable is the use of OCA initiated at the index date.

Covariates:

The following covariates/control variables will be assessed **in the pre-index period**, utilizing the value closest to the index date:

- Age at index date
- Sex
- Most recent liver biochemistry levels (TB, ALP, ALT, AST)
- Most recent platelet counts
- Time (in months) since UDCA failure
- Clinical evidence of portal hypertension (platelets <150,000 and/or non-bleeding varices)
- Cirrhosis
- Most recent Charlson Comorbidity Index Score
- Insurance type at index date (Komodo Health only)

Statistical Methods:

Analysis Populations

The statistical analysis of the HEROES PBC studies will follow a nested randomized trial emulation approach (Hernán 2008, Danaei 2013) using a treatment decision design to identify index events (Brookhart 2015). Due to the lack of randomization, non-randomized observational studies will instead be conducted, with the goal of mimicking the hypothetical randomized trial as closely as possible. All patients will be evaluated over time from the start of the study period to identify evidence of inadequate treatment response to UDCA. Each date of inadequate response identified in the data will be considered a treatment decision point, and that date will be considered an index date, with a corresponding record created in the analytic data for that patient index. Each patient can contribute multiple index dates and thus patient indices, corresponding to each date they have a treatment decision point, and therefore each patient may contribute person-time to multiple patient index records.

It is likely that OCA-treated and non–OCA-treated patient indices will differ on confounding variables, ie, variables that influence both treatment and outcome. To address differences in the covariate distribution between treatment groups, the Sponsor will first conduct descriptive analyses on all baseline variables (demographics, clinical characteristics, and treatment history) for the OCA-treated and non–OCA-treated groups at index. Standardized mortality/morbidity ratio (SMR) weights then will be used to create a pseudo-population of non–OCA-treated indices with the same covariate distribution as the OCA-treated patients at the time of OCA initiation (Sato 2003), and unweighted and weighted standardized mean differences will be computed.

Primary Analysis:

The objective of the primary analysis is to estimate the as-treated effect of OCA treatment versus non–OCA-based treatment on the composite endpoint of all-cause death, liver transplant, or decompensation requiring hospitalization. The primary analysis outcome will be assessed with the hazard ratio comparing the hazard of the first event of the composite endpoint among the OCA-treated patients and standardized morbidity ratio-weighted

non–OCA-treated PBC patient indices. The hazard ratio will be estimated using a Cox proportional hazards model. The nonparametric bootstrap will be used to estimate the standard error of the estimate, which will then be used to generate 95% CI for the hazard ratio and to perform a test of the hypothesis that the hazard ratio is equal to the null value of 1.

Exploratory Analysis:

The exploratory objectives are to estimate the effect of OCA treatment versus non-OCA treatment on each component of the composite endpoint (all-cause death, liver transplant, or hepatic decompensation). The exploratory analysis outcomes will be assessed with the subdistribution hazard ratio comparing the hazard of the first event of each element of the composite endpoint, separately, among the OCA-treated patients and standardized morbidity ratio-weighted non–OCA-treated PBC patient indices. For the endpoint of liver transplant, death will be treated as a competing event. For the endpoint of hepatic decompensation, death and liver transplant will be treated as competing events. The subdistribution hazard ratio will be estimated using a Fine-Gray proportional subdistribution hazards model. The nonparametric bootstrap will be used to estimate the standard error of the estimates, which will then be used to calculate 95% CI for the hazard ratio and perform a test of the hypothesis that the hazard ratio is equal to the null value of 1.

Sample Size Justification:

Using the expected sample size in the 2 populations, the Sponsor computed power to detect treatment effects (relative hazards) of varying sizes, estimated using Cox proportional hazards regression. Computations are based on the formulae of Schoenfeld 1983. To account for confounding control due to the application of IP weights, the Sponsor inflated the variance from the Schoenfeld formula using factors derived by Shook-Sa 2020. It was conservatively assumed just one control observation per patient. In the Komodo Health data, a preliminary investigation found that approximately 395 patients who meet entry criteria initiate OCA and that 5916 patients will contribute at least one record to the control group (UDCA nonresponders). In the Global PBC registry, the Sponsor expects to have 344 patients meeting entry criteria who initiate OCA, and 2200 who contribute at least one observation to the control group. Power in both cohorts was computed for relative hazards ranging from 0.5 to 0.9 with an alpha level of 0.05. The Sponsor considered baseline event rates during follow-up from 5% to 15% and variance inflation corresponding to mild confounding (VIF=1.05), moderate confounding (VIF=1.5), and strong confounding (VIF=2.0). In each study, power was plotted under these assumptions against a reference line of 80% power under moderate confounding (VIF=1.5).

Under mild confounding, both studies will be well-powered to detect an HR of 0.5. For moderate confounding, the Komodo Health study will be adequately powered to detect HR of 0.5 for event rates >6%. The Global PBC registry will be adequately powered to detect event rates >8%. Under strong confounding, the Komodo Health study will be adequately powered to detect HR of 0.5 for event rates >9%. The Global PBC registry will be adequately powered to detect HR of 0.5 for event rates >9%. The Global PBC registry will be adequately powered to detect HR of 0.5 for event rates >9%. The Global PBC registry will be adequately powered to detect event rates >11%. Power decreases for more moderate HRs. None of the studies under even the most favorable assumptions will be able to detect HRs of 0.9. The Sponsor notes that the assumptions made here are conservative; in particular, it is expected that many more than one control observation and that the addition of lab data from LabCorp to will substantially increase the size of both treatment groups in the Komodo Health study.

Subgroup Analyses:

The entire analysis will be repeated separately by patient race (Komodo Health only), age (categorical), sex, region, presence/absence of cirrhosis, and pre-/post-COVID. Because race is not completely captured in either database, these analyses will only include those with non-missing values for race.

Sensitivity Analyses:

- An analysis will be conducted in the Komodo database to assess the performance of a claims-based PBC definition with AMA test results as the gold standard.
- Quantitative bias analysis to quantify the sensitivity of the estimate to violations of the assumption of no unmeasured confounding.

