7. SELECTION OF PATIENTS

7.1. Study Population

All patients who meet diagnostic criteria in each database between 01 Jun 2015 and 31 Dec 2021 and who meet the eligibility criteria will be considered for these studies.

All diagnosis, treatment, laboratory, and procedure codes used to identify patients and define study variables are listed in Appendix A.

The treatment group will be patients with PBC with a history of inadequate response or intolerance to UDCA who initiated OCA in the study window. The control group will be PBC patients with a history of inadequate response or intolerance to UDCA who were eligible but were not treated with OCA (or off-label fibrates) in the study window. The decision to treat a patient with OCA or UDCA is at the discretion of the treating physician and has been made independent from inclusion in each of the databases.

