7.3. Exclusion Criteria

A patient who meets **any** of the following criteria for a given index date is not eligible for inclusion:

- History or presence of other concomitant liver diseases before the index date (inclusive), including:
 - Acute or chronic hepatitis C virus infection
 - Acute or chronic hepatitis B infection

- Primary sclerosing cholangitis
- Active alcoholic liver disease
- Hepatocellular carcinoma
- Hepatorenal syndrome
- Hepatopulmonary syndrome
- Portopulmonary syndrome
- NASH
- History of non-skin malignancy or melanoma before the index date (inclusive)
- History of HIV before the index date (inclusive)
- Medical conditions that may cause non-hepatic increases in ALP:
 - Paget's disease during the 12-month period before the index date (inclusive)
 - Fractures within 3 months before the index date (inclusive)
- Patients with laboratory values indicative of hepatic decompensation or significant hepatobiliary injury before the index date (inclusive):
 - TB >3 mg/dL
 - ALP >10x ULN
 - ALT and/or AST >10x ULN
- History of liver transplant before the index date (inclusive)
- Evidence of OCA, fenofibrate, or bezafibrate use before the index date (inclusive)
- History or presence of any of the following hepatic decompensating events before the index date (inclusive):
 - Variceal bleeding
 - Ascites
 - Hepatic hydrothorax
 - Spontaneous bacterial peritonitis
 - Hepatic encephalopathy

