 - Komodo Health: The Komodo Health data has been linked to the US National Death Index (NDI), and mortality will be recorded as date of death as recorded in the Index
 - Global PBC registry: Death and date of death are reported by the physician via electronic Case Report Form (eCRF) and recorded through the CASTOR trial platform
- Liver transplantation
 - Komodo Health: The Komodo Health data will be linked to the OPTN database to ascertain whether a patient has received a liver transplant and the date of transplant.
 - Global PBC registry: Liver transplant and date of transplant are reported by the physician via eCRF and recorded through the CASTOR trial platform.
- Hospitalization for hepatic decompensation
 - Komodo Health: Hospitalization for hepatic decompensation will be assessed by any hospital admission claim with the following International Classification of Diseases (ICD)-10 codes (in any position) for decompensating events
 - Variceal bleed: ICD-10: I85.01, I85.11, I86.4 and ICD-9: 456.1, 456.21, 456.8
 - Ascites: ICD-10: K70.11, K70.31, K71.51, R18.0, R18.8, J94.8, K65.2 and ICD-9: 567.23, 571.2, 789.51,789.59, 511.8, 567.23

- Hepatic encephalopathy: ICD-10: B15.0, B16.0, B16.2, B17.11, B19.0, B19.11, B19.21, K70.41, K72.11, K72.90, K72.91 and ICD-9: 572.2, 070.0, 070.20, 070.41, 070.6, 070.71; or utilization of lactulose and/or rifaximin.
- Global PBC registry: Hospitalization for hepatic decompensation and date of hospitalization are reported by the physician via eCRF and recorded through the CASTOR trial platform

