APPENDIX A. LIST OF INCLUSION, EXCLUSION AND COVARIATE CODES

INCLUSION/EXCLUSION CRITERIA CODES

CODE	ТҮРЕ	DESCRIPTION		
Inclusion c	riteria			
K74.3	ICD10	Primary biliary cholangitis		
571.6	ICD9	Biliary cirrhosis (for rule-out in the baseline period)		
Exclusion of	criteria			
0FY00Z1	ICD10 pcs	Transplantation of liver, syngeneic, open approach		
0FY00Z0	ICD10 pcs	Transplantation of Liver, Allogeneic, Open Approach		
47135	HCPCS/ CPT-4	Liver allotransplantation; orthotopic; partial or whole, from cadaver or living donor, any age		
B17.10	ICD10	Acute hepatitis C without hepatic coma		
B17.11	ICD10	Acute hepatitis C with hepatic coma		
070.41	ICD9	Acute hepatitis C with hepatic coma		
070.51	ICD9	Acute hepatitis C without mention of hepatic coma		
B18.2	ICD10	Chronic viral hepatitis C		
070.44	ICD9	Chronic hepatitis C with hepatic coma		
070.54	ICD9	Chronic hepatitis C without mention of hepatic coma		
070.70	ICD9	Unspecified viral hepatitis C without hepatic coma		
070.71	ICD9	Unspecified viral hepatitis C with hepatic coma		
B16.0	ICD10	Acute hepatitis B with delta-agent with hepatic coma		
B16.1	ICD10	Acute hepatitis B with delta-agent without hepatic coma		
B16.2	ICD10	Acute hepatitis B without delta-agent with hepatic coma		
B16.9	ICD10	Acute hepatitis B without delta-agent and without hepatic coma		
B17.0	ICD10	Acute delta-(super) infection of hepatitis B carrier		
070.20	ICD9	Viral hepatitis B with hepatic coma, acute or unspecified, without mention of hepatitis delta		
070.21	ICD9	Viral hepatitis B with hepatic coma, acute or unspecified, with hepatitis delta		
070.30	ICD9	Viral hepatitis B without mention of hepatic coma, acute or unspecified, without mention of hepatitis delta		
070.31	ICD9	Viral hepatitis B without mention of hepatic coma, acute or unspecified, with hepatitis delta		
B18.0	ICD10	Chronic viral hepatitis B with delta-agent		
B18.1	ICD10	Chronic viral hepatitis B without delta-agent		
070.23	ICD9	Chronic viral hepatitis B with hepatic coma with hepatitis delta		
070.22	ICD9	Chronic viral hepatitis B with hepatic coma without hepatitis delta		
070.33	ICD9	Chronic viral hepatitis B without mention of hepatic coma with hepatitis delta		
070.32	ICD9	Chronic viral hepatitis B without mention of hepatic coma without mention of hepatitis delta		
K83.01	ICD10	Primary sclerosing cholangitis (2019-2021 only)		
K70.0	ICD10	Alcoholic fatty liver		

CODE	ТҮРЕ	DESCRIPTION
K70.10	ICD10	Alcoholic hepatitis without ascites

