814	ICD9	Fracture of carpal bone(s)
815	ICD9	Fracture of metacarpal bone(s)
816	ICD9	Fracture of one or more phalanges of hand
817	ICD9	Multiple fractures of hand bones
818	ICD9	Ill-defined fractures of upper limb
819	ICD9	Multiple fractures involving both upper limbs and upper limb with rib(s) and sternum
820	ICD9	Fracture of neck of femur
821	ICD9	Fracture of other and unspecified parts of femur
822	ICD9	Fracture of patella
823	ICD9	Fracture of tibia and fibula
824	ICD9	Fracture of ankle
825	ICD9	Fracture of one or more tarsal and metatarsal bones
826	ICD9	Fracture of one or more phalanges of foot
827	ICD9	Other multiple and ill-defined fractures of lower limb
828	ICD9	Multiple fractures involving both lower limbs lower with upper limb and lower limb(s) with rib(s) and sternum
829	ICD9	Fracture of unspecified bones

CODE	ТҮРЕ	DESCRIPTION
I85.01	ICD10	Esophageal varices with bleeding
I85.11	ICD10	Secondary esophageal varices with bleeding
456.0	ICD9	Esophageal varices with bleeding
K70.11	ICD10	Alcoholic hepatitis with ascites
K70.31	ICD10	Alcoholic cirrhosis of liver with ascites
K71.51	ICD10	Toxic liver disease with chronic active hepatitis with ascites
R18.0	ICD10	Malignant ascites
R18.8	ICD10	Other ascites
571.2	ICD9	Alcoholic cirrhosis of liver
789.51	ICD9	Malignant ascites
789.59	ICD9	Other ascites
J94.8	ICD10	Other specified pleural conditions
511.8	ICD9	Other specified forms of pleural effusion, except tuberculous
567.23	ICD9	Spontaneous bacterial peritonitis
K65.2	ICD10	Spontaneous bacterial peritonitis
B15.0	ICD10	Hepatitis A with hepatic coma
B16.0	ICD10	Acute hepatitis B with delta-agent with hepatic coma
B16.2	ICD10	Acute hepatitis B without delta-agent with hepatic coma
B17.11	ICD10	Acute hepatitis C with hepatic coma
B19.0	ICD10	Unspecified viral hepatitis with hepatic coma
B19.11	ICD10	Unspecified viral hepatitis B with hepatic coma
B19.21	ICD10	Unspecified viral hepatitis C with hepatic coma
K70.41	ICD10	Alcoholic hepatic failure with coma
K72.11	ICD10	Chronic hepatic failure with coma
K71.11	ICD10	Toxic liver disease with hepatic necrosis, with coma
K72.01	ICD10	Acute and subacute hepatic failure with coma
K72.91	ICD10	Hepatic failure, unspecified with coma
572.2	ICD9	Hepatic encephalopathy
070.0	ICD9	Viral hepatitis A with hepatic coma
070.21	ICD9	Viral hepatitis B with hepatic coma, acute or unspecified, with hepatitis delta
070.20	ICD9	Viral hepatitis B with hepatic coma, acute or unspecified, without mention of hepatitis delta

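### Komodo only: Appendix A excludes unspecified hepatitis B and C without coma under ICD-9 but has no matching ICD-10 row, so the same diagnosis is handled differently by code system

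*Combined protocol and SAP*

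**What the plan says.** The Synopsis and Section 7.3 exclude, at each index date, patients with a history of "Acute or chronic hepatitis C virus infection" or "Acute or chronic hepatitis B infection". Section 7.1 names the operative list: "All diagnosis, treatment, laboratory, and procedure codes used to identify patients and define study variables are listed in Appendix A".

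In the Appendix A exclusion block:

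- The ICD-10 hepatitis C rows are B17.10 and B17.11 (acute) and B18.2, labelled "Chronic viral hepatitis C".
- The ICD-10 hepatitis B rows are B16.0, B16.1, B16.2, B16.9 and B17.0 (acute), B18.0, and B18.1, labelled "Chronic viral hepatitis B without delta-agent".
- The ICD-9 rows go further. They include 070.70, labelled "Unspecified viral hepatitis C without hepatic coma", and four hepatitis B codes (070.20, 070.21, 070.30, 070.31) whose labels cover acute and unspecified infection together.
- Unspecified hepatitis B or C in ICD-10 appears only among the decompensation rows and only with coma: B19.11, and B19.21, labelled "Unspecified viral hepatitis C with hepatic coma".

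Sections 8.1 and 12.4.3 then use the with-coma codes as outcomes. The encephalopathy list contains the run "B19.0, B19.11, B19.21, K70.41, K72.11, K72.90, K72.91".

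**The concern.** One exclusion is applied through two code lists that do not mean the same thing. A record of unspecified hepatitis C without coma removes the patient if coded in ICD-9 and leaves the patient in if coded in ICD-10. The looser list does most of the work: Komodo data begin in June 2015 (Section 12.1.1), index dates begin on 01 Jun 2016 (Section 7.6), and Section 12.4.3 treats ICD-10 as the standard for US claims.

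A retained patient can meet the UDCA failure definition because Section 7.1.1 needs only one ALP or bilirubin value above ULN after the required UDCA exposure, and viral hepatitis can contribute to such a value. Under Section 7.4 each qualifying date can open a control index, and the patient can equally enter at OCA initiation. A later admission coded B19.11 or B19.21 would then enter a PBC endpoint as an encephalopathy event although the code names a viral cause.

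**Working it through.** **Step 1: set the code lists side by side.** All rows come from the Appendix A exclusion block, including its decompensation rows.

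| Meaning | ICD-9 rows | ICD-10 rows |
|---|---|---|
| Hepatitis C, acute | 070.41, 070.51 | B17.10, B17.11 |
| Hepatitis C, chronic | 070.44, 070.54 | B18.2 |
| Hepatitis C, unspecified, with coma | 070.71 | B19.21 (decompensation rows) |
| Hepatitis C, unspecified, no coma | 070.70 | none |
| Hepatitis B, acute | 070.20, 070.21, 070.30, 070.31 (shared with unspecified) | B16.0, B16.1, B16.2, B16.9, B17.0 |
| Hepatitis B, chronic | 070.22, 070.23, 070.32, 070.33 | B18.0, B18.1 |
| Hepatitis B, unspecified, with coma | 070.20, 070.21 | B19.11 (decompensation rows) |
| Hepatitis B, unspecified, no coma | 070.30, 070.31 | none |

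Two cells are empty, both for unspecified infection without coma. No row elsewhere in Appendix A fills them.

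**Step 2: who is affected.** Only patients whose sole hepatitis B or C record is the unspecified ICD-10 code without coma. Any listed acute, chronic or ICD-9 code still excludes the patient, and so does a with-coma code before index. The registry study records its data by eCRF and is not touched.

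**Step 3: what adjusts for them.** Section 10.1.1 has no viral hepatitis covariate. It does include bilirubin, ALP, ALT, AST, platelets, portal hypertension and cirrhosis, and Section 10.2 also puts baseline covariates in the Cox model.

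**Step 4: possible size.** The plan states no figure to reproduce. Section 10.9 gives the formula

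bias factor = (OR × P1 + 1 − P1) / (OR × P0 + 1 − P0),

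where OR is the association of the unmeasured factor with the outcome after adjustment for known confounders, and P1 and P0 are its prevalence in OCA-treated and control indices. The inputs below are assumptions; the documents supply none.

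| OR | P1 | P0 | Arithmetic | Factor |
|---|---|---|---|---|
| 1.5 | 0 | 1% | 1 / 1.005 | 0.995 |
| 3 | 0 | 5% | 1 / 1.10 | 0.909 |
| 3 | 1% | 3% | 1.02 / 1.06 | 0.962 |
| any | 1% | 1% | equal terms | 1.000 |
| 1.5 | 3% | 1% | 1.015 / 1.005 | 1.010 |
| 3 | 3% | 1% | 1.06 / 1.02 | 1.039 |

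The factor multiplies the true ratio. It falls below 1 only if affected patients are commoner among controls, and above 1 if they are commoner among OCA patients.

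**The case against.** The best defence is that the criterion, as worded, names acute and chronic infection, and the ICD-10 rows deliver exactly that. For hepatitis B this has force: the ICD-9 codes combine acute and unspecified infection, so a sponsor excluding acute disease could not avoid taking the unspecified cases too, and those rows show little about intent. It does not hold for hepatitis C. Code 070.70 is purely unspecified and was listed as an exclusion, so the sponsor's own list treats it as meeting the rule.

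A second defence is that Appendix A may not be complete. It contains no codes for OCA, UDCA or fibrates, and the laboratory test codes sit in Section 12.4.4. Absence from the list is therefore strong evidence, not proof, that a code is not applied. Section 7.1 nevertheless presents the list as complete, so the list should be put right.

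Third, Section 10.9 plans a bias analysis, and Section 10.11 lets the Clean Room Committee revise definitions without outcome results by group. Both limit the consequence. Neither closes this gap.

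Two stronger readings are tempting and not supported. A reader might infer that the hazard ratio is biased in favour of OCA. That requires affected patients to be commoner among controls, and nothing in the documents says so; the same list applies to both groups. A reader might also count the absence of an ICD-10 unspecified hepatitis row from the Charlson codes as a further gap. The Charlson liver rows already list the whole K74 family, the parent of the PBC inclusion code K74.3. Read by category, every such patient already scores there, and an added hepatitis row would change nothing.

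**Conclusion.** The inconsistency is real and can be read directly from Appendix A; it is plain for hepatitis C and less clear for hepatitis B. It concerns Komodo alone and a subgroup of unknown size. It would be too strong to call the condition wholly unadjusted: there is no hepatitis-specific term, but the liver covariates in the weights and the outcome model may capture part of its effect.

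The direction of any bias is not known. The range of about 0.91 to 1.04 rests entirely on assumed odds ratios of 1.5 to 3 and assumed prevalences of 0 to 5%; the likely effect is small. The case for acting is that the same diagnosis should not be kept or removed according to code system, and that the repair costs little while outcomes are still blinded. After unblinding it would be a change to cohort membership made with results in view.

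**What to change.** Before the Komodo cohort is locked and the event file is released under Section 10.1.2:

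1. Add to the Appendix A exclusion block the ICD-10 rows for unspecified viral hepatitis B and unspecified viral hepatitis C, each without hepatic coma.
2. Apply them at every index date, in both groups.
3. Check that each ICD-9 exclusion row has an ICD-10 row of the same meaning, and record the result in the study log.
4. Rerun the cohort counts and report how many patients and indices the new rows remove, by group.

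If the sponsor prefers to keep such patients, the alternative is to say so in Section 7.3 and explain why 070.70 is listed. The cost is two added entries, one rerun of the counts and a small loss of patients. No outcome data are needed.
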